# **Intestinal Microbiota Transplantation for Nonalcoholic Fatty Liver Disease (NAFLD)**

**Date:2017.5**

## 1.Method

Intestinal microbiota transplantation(IMT) refers to make fecal from the health into a suspension of microbes through an intelligent bacteria processing system, and then infuse the suspension into the gastrointestinal tract of patients through nasso intestinal tube, gastroscope, enteroscope or capsule intake which can reconstruct intestinal microbiota and play the role of treatment without obvious side effect.

## 2.Plan

### 1)Patient recruitment

Inclusion Criteria:

- subjects with NAFLD(nonalcoholic fatty liver disease)
- aged 18-65
- $24 \leq \text{BMI}$
- liver/spleen (L/S) ratio no more than 0.7 by CT scan

Exclusion Criteria:

- Alcoholic liver disease (ALD), chronic hepatitis C, autoimmune liver disease, Wilson's disease
- Drug treatment (tamoxifen, amiodarone, sodium valproate, methotrexate, glucocorticoids, etc.),total parenteral nutrition, inflammatory bowel disease, hypothyroidism, Cushing's syndrome, beta lipoprotein deficiency, IR related syndromes (lipid wasting diabetes mellitus, Mauriac syndrome), gastrointestinal surgery
- Hepatocellular carcinoma (HCC), biliary tract diseases and taking or taking chinese and western medicines that can lead liver enzymes elevation in the near future.
- Moderate and severe renal injury (serum creatinine $>2\text{mg/dL}$  or  $177\text{mmol/L}$ ), moderate and severe chronic obstructive pulmonary disease, severe hypertension, cerebrovascular accident,congestive heart failure, unstable angina pectoris.
- Antibiotics treatment in 7 days before recruited and unwilling to stop it, long-term lipid-lowering drugs, antidiabetic drugs and other liver protecting drugs treatment
- Antibiotics, other probiotics, gastrointestinal motility drugs and other preparation that may influence intestinal microbiota treatment
- Other serious diseases that may interfere the recruitment or affect the survival, such as cancer or acquired immune deficiency syndrome
- Mentally or legally disabled person
- Preparing for pregnancy
- Medical or social condition which in the opinion of the principal investigator would interfere with or prevent regular follow up articipating in other clinical trials.

Recruit the patients who meet the inclusion criteria, and fail to meet the exclusion

criteria. Introduce this clinical trial to the patients and obtain the informed consent. Assess the condition of the disease.

## 2) Arms and Interventions

Randomly divided the patients into experimental arm and control arm and intervene them as described in the following table.

arms	Assigned interventions
Experimental: IMT  30 non-alcoholic fatty liver disease (NAFLD) patients will be recruited for the study, which involved a 6 times intestinal microbiota transplant(IMT) and the time interval is generally 2 weeks.  Interventions:  Procedure: Intestinal Microbiota Transplantation	intestinal microbiota transplant intestinal microbiota transplantation Participants in Experimental group take 6 times IMT with 2-week intervals
Agents  30 non-alcoholic fatty liver disease (NAFLD) patients without any treatment	

## 3) Outcome Measures

### Primary Outcome Measure:

- ① The change of CT ratio of liver/spleen  
CT imaging has been used to assess hepatic steatosis and has been validated in relation to liver biopsy. The ratio of liver to spleen (L/S ratio) for CT attenuation values is an index, with a L/S ratio<1 considered to represent fatty liver. The
- ② change of CT ratio of liver/spleen will be assessed at different time comparing with the baseline.

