### Secondary Outcome Measure:

- ① general indicators  
Basic information and symptoms will be assessed at different time comparing with the baseline  
[Time Frame: 3 months, 6months]
- ② biochemical indicators

Liver function will be assessed at different time comparing with the baseline

[Time Frame: 3 months, 6months]

③ Fibroscan E value

Fibroscan E value is indicators for evaluating liver fibrosis. Changes will be assessed at different time comparing with the baseline

[Time Frame: 3 months, 6months]

④ Changes of gut microbiota

Alpha and Beta diversity of GI microbiota by High-throughput sequencing on baseline

line and 3 months,6months after treatment.

[Time Frame: 3 months, 6months]

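### The trial is open, and the protocol provides no masking of the CT reading that produces its only primary outcome

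*Protocol*

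**What the plan says.** Under Arms and Interventions the protocol randomises: "Randomly divided the patients into experimental arm and control arm". The experimental arm is described as "Participants in Experimental group take 6 times IMT with 2-week intervals". The control arm is "30 non-alcoholic fatty liver disease (NAFLD) patients without any treatment". No sham or placebo transplant is described.

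Under Primary Outcome Measure the endpoint is "The change of CT ratio of liver/spleen", compared with baseline at times that are not given. The section carries two item numbers, but both concern this one ratio, so it is the sole primary outcome. The measurement is described only as far as "The ratio of liver to spleen (L/S ratio) for CT attenuation values is an index".

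The same ratio is an inclusion criterion (at most 0.7 on CT), so a CT reading exists from screening. Nowhere does the protocol mention masking, blinding, independent reading or a rule for placing the liver and spleen regions.

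**The concern.** Six procedures against none, without a sham, makes the trial open to patients and treating staff. Whoever reads the scans is masked only if someone takes a deliberate step, and the protocol asks for none.

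An attenuation value is a number from the scanner, but the ratio depends on where the liver and spleen regions are placed. With no placement rule, the numerator and the denominator both leave room for judgement. A reader who expects improvement after transplantation could place regions slightly differently in that arm. Such a shift acts in one direction on the only primary outcome, and a larger sample does not average it out.

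This is not a matter left to an SAP. Who reads the scans, and with what knowledge, is trial conduct. An SAP analyses the readings it receives and cannot take expectation out of them afterwards.

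**Working it through.** **No stated figure to reproduce.** The protocol gives 30 patients per arm, but no alpha, power, effect size or SD. What follows is an illustration.

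**Which shifts matter.** Write the change as the follow-up ratio minus the baseline ratio.
- *Arm-related shift.* The recruitment step, with its eligibility CT, is set out before the allocation. The screening reading should therefore precede randomisation and be free of knowledge of arm, while follow-up readings need not be. An arm-related shift at follow-up then enters the change in full and is not cancelled by baseline.
- *Visit-only shift.* If every follow-up scan is read higher by the same amount in both arms, the shift cancels in the between-arm difference. It stays in the change from baseline within each arm, which is what the primary outcome text describes.

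**Inputs**
- From the protocol: 30 per arm; entry ratio at most 0.7.
- Assumed: spleen attenuation 50 HU; SD of the change in ratio 0.15, 0.20 or 0.25; two-sided alpha 0.05; mean arm-related shift in the liver reading of 0 to 3 HU.

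**Formulas** (normal approximation, no true effect)
- SE = SD × √(2/30), which is 0.039, 0.052 and 0.065 for the three SDs.
- Bias in the ratio = HU shift / 50, which is 0.02, 0.04 and 0.06 for 1, 2 and 3 HU.
- Type I error = P(Z > 1.96 − bias/SE) + P(Z < −1.96 − bias/SE).

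**Worked case.** For 2 HU and SD 0.20, bias/SE = 0.04/0.0516 = 0.77. The type I error is P(Z > 1.19) + P(Z < −2.73) = 0.118 + 0.003 = 12.1%.

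| Arm-related liver shift | Bias in ratio | SD 0.15 | SD 0.20 | SD 0.25 |
|---|---|---|---|---|
| 0 HU | 0 | 5.0% | 5.0% | 5.0% |
| 1 HU | 0.02 | 8.1% | 6.7% | 6.1% |
| 2 HU | 0.04 | 17.8% | 12.1% | 9.5% |
| 3 HU | 0.06 | 34.1% | 21.3% | 15.3% |

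At 2 and 3 HU, nearly all of these false positives favour transplantation if the shift does.

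**Scale.** With 30 per arm, the difference detectable with 80% power is (1.96 + 0.84) × √(2/30) = 0.72 SD, or 0.108 to 0.181 in ratio units for SD 0.15 to 0.25. A bias of 0.04 is 37% to 22% of that. The spleen reading matters too: with an assumed liver value of 35 HU, reading the spleen at 48 instead of 50 HU moves the ratio from 0.700 to 0.729.

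**After the fix.** If masked reading removes the arm-related shift, the calculation returns to the 0 HU row. The sample size does not change.

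**The case against.** The strongest reply is that the protocol is silent, which is different from prescribing an unmasked reading. That stands. A reader might infer that the person reading the CT knows the arm, but the document does not support this. It shows that patients and treating staff know the arm, and says nothing about the reader. A site could follow the text with a masked or an unmasked reader. The point is that the text provides no safeguard.

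A second reply is that attenuation is numeric, and that every bias input apart from the 30 per arm is assumed. This also stands. Region placement leaves room for bias, but nothing in the protocol shows how much. At 0.5 HU the same formula gives only 5.3-5.8%, so the larger percentages reflect the shifts chosen and are not estimates.

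Two further inferences should be resisted:
- Reading without masking to visit does not by itself bias the comparison between arms, because a shift equal in both arms cancels there.
- CT is not the only assessment that could be masked cheaply. The liver function tests and the microbiota sequencing among the secondary outcomes could be run on coded samples. CT is singled out because it carries the primary outcome.

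**Conclusion.** The point holds as a gap in trial conduct: an open trial whose sole primary outcome depends on a reading that the protocol does not mask. Arm-related reading bias is possible in the follow-up ratios and would bias the between-arm comparison. Visit-related bias is possible in the within-arm change.

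The size is unknown. Under the stated assumptions the false-positive rate runs from 5% with no shift, through about 6-8% at 1 HU, to 10-18% at 2 HU and 15-34% at 3 HU. The protocol supports neither a claim that readers are in fact unmasked nor a claim that such a bias will occur.

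The change is a cheap improvement worth making. It would not remove other effects of an open, untreated control, such as differences in diet, weight or co-treatment.

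**What to change.** Add to the primary outcome:

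> All CT scans, including baseline, are de-identified, put in random order and read in one batch by the site's CT reader, masked to arm and visit, using the same liver and spleen region rule for every scan. These readings are used for the primary analysis, and the live screening reading is used only for eligibility.

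The protocol names no reader. If the site's reader has already seen some scans live, a few may be recognised; de-identification and random order reduce that risk.

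**Cost.** One protocol sentence on reading, one on use, a written region rule, and a batch re-read of scans already taken. That is about 60 × 3 = 180 scans if CT is done at baseline, 3 and 6 months. The two follow-up times are borrowed from the secondary outcomes, because none are given for CT. No extra scan, visit or patient is needed. The drawback is that the primary readings become available later.

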### Secondary Outcome Measure:

- ① general indicators  
Basic information and symptoms will be assessed at different time comparing with the baseline  
[Time Frame: 3 months, 6months]
- ② biochemical indicators

Liver function will be assessed at different time comparing with the baseline

[Time Frame: 3 months, 6months]

③ Fibroscan E value

Fibroscan E value is indicators for evaluating liver fibrosis. Changes will be assessed at different time comparing with the baseline

[Time Frame: 3 months, 6months]

④ Changes of gut microbiota

Alpha and Beta diversity of GI microbiota by High-throughput sequencing on baseline

line and 3 months,6months after treatment.

[Time Frame: 3 months, 6months]

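### Does timing the microbiota samples from treatment leave their schedule unusable, when treatment is a six-procedure course and controls receive none?

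*Protocol*

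**What the plan says.** Under Secondary Outcome Measure, the fourth outcome (changes of gut microbiota) is described as "Alpha and Beta diversity of GI microbiota by High-throughput sequencing on baseline", followed by "line and 3 months,6months after treatment". The stray first word of the second quote is a broken repeat of baseline and plays no part here. The outcome carries the label "Time Frame: 3 months, 6months", as do the other three secondary outcomes. Those three do not mention treatment in their timing. The Fibroscan outcome, for example, says "Changes will be assessed at different time comparing with the baseline".

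Section 2) Arms and Interventions defines the treatment: "Participants in Experimental group take 6 times IMT with 2-week intervals". The same table is less strict about spacing: "the time interval is generally 2 weeks". The control arm is "30 non-alcoholic fatty liver disease (NAFLD) patients without any treatment".

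Section 1.Method says that IMT "can reconstruct intestinal microbiota and play the role of treatment". The microbiota outcome is the only listed outcome that measures the first half of that claim.

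**The concern.** A time counted from treatment needs a treatment date. The experimental arm has six of them, spread over about 10 weeks, and the control arm has none. A strict reader could therefore find two origins in one arm and no origin in the other.

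The two origins answer different questions. Counted from baseline, the month-3 sample shows the gut shortly after the last infusion. Counted from the end of the course, it shows whether any change has lasted about three months. If the baseline schedule were run but reported in the Protocol's words, a reader could think that more time had passed since the last IMT than really had. The worst case would be counting IMT patients from their last procedure and controls from baseline, because the arms would then be sampled at different study times.

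**Working it through.** The Protocol states no derived figure to reproduce, so the check is date arithmetic.

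**Inputs from the Protocol**
- Number of IMTs: 6 (section 2, Arms and Interventions).
- Interval: 2 weeks, described as general rather than fixed (same section).
- Sampling: baseline, 3 months, 6 months (Secondary Outcome Measure).

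**Assumptions, not in the Protocol**
- The first IMT is on the day of baseline.
- Months are calendar months: 3 × 365.25 / 12 / 7 = 13.04 weeks and 6 × 365.25 / 12 / 7 = 26.09 weeks. The alternative is 4-week months: 12 and 24 weeks.

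**Course length**

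(6 − 1) × 2 = 10 weeks from first to last IMT.

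**The two readings**

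| Visit | Counted from baseline: weeks after last IMT | Counted from last IMT: weeks after it (study week) |
|---|---|---|
| Month 3 | 13.04 − 10 = 3.04 | 13.04 (13.04 + 10 = 23.04) |
| Month 6 | 26.09 − 10 = 16.09 | 26.09 (26.09 + 10 = 36.09) |

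The readings differ by 10 weeks at each visit. With 4-week months, month 3 is 12 − 10 = 2 weeks or 12 weeks after the last IMT, and month 6 is 24 − 10 = 14 or 24 weeks. The difference is again 10 weeks.

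**Sensitivity to the interval (counted from baseline, calendar month 3)**

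| Interval (weeks) | Last IMT at week | Weeks from last IMT to sample |
|---|---|---|
| 1.5 | 5 × 1.5 = 7.5 | 13.04 − 7.5 = 5.54 |
| 2 | 5 × 2 = 10 | 13.04 − 10 = 3.04 |
| 2.5 | 5 × 2.5 = 12.5 | 13.04 − 12.5 = 0.54 |
| 3 | 5 × 3 = 15 | 13.04 − 15 = −1.96 (sample precedes last IMT) |

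The figure of about 3 weeks therefore depends on near-exact 2-week spacing. So does the 10-week difference between readings, which equals the course length: 7.5 weeks at 1.5-week spacing and 15 weeks at 3-week spacing. A delay before the first IMT also matters. With an assumed 2-week delay the last IMT is at week 12, the month-3 sample falls 13.04 − 12 = 1.04 weeks later, and the readings differ by 12 weeks.

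**Difference between arms**

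On a baseline schedule for everyone, both arms are sampled at week 13.04: difference 0. On an end-of-course schedule applied to everyone, both are sampled at week 23.04: difference 0. Only separate clocks would put the arms 23.04 − 13.04 = 10 weeks apart, and nothing in the Protocol says that the arms run on separate clocks.

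**Reading the text as a whole**

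The time-frame label names no origin, so it does not contradict the words about treatment. It is, however, identical across all four secondary outcomes, and the microbiota outcome lists baseline, 3 months and 6 months in sequence. The simplest reading is one series of visits for all outcomes and both arms, with the mention of treatment standing loosely for follow-up after baseline. On that reading, controls have a perfectly definite sampling date.

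**The case for a change.** The best case for a change is this. The Protocol is the document that governs when stool is collected, and no later analysis plan can recover a sample taken at the wrong time. The microbiota outcome is the only secondary outcome whose timing is tied to treatment, so the phrase might be deliberate. References to baseline in the other outcomes name the comparator and do not strictly start the clock. The outcome also tests the mechanism on which the intervention rests, and a clearer sentence would cost nothing.

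Much of this stands. The origin is not written down, the phrase fits controls badly, and early effect and persistence are different questions. It does not, however, show that anything goes wrong. Either schedule is sensible, either gives both arms the same sampling weeks, and neither adds or loses a visit. Asking the sponsor to choose one is asking for a detail to be written out, not for a faulty choice to be corrected. The risk of misreading the time since the last IMT arises only if the report repeats the loose phrase, and giving the actual dates removes it. Visit definitions are also commonly set in the analysis plan, which is not at hand.

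**Conclusion.** No change to the plan follows. This is a minor ambiguity of wording in one secondary outcome, and analysts can settle it sensibly by treating the visits as 3 and 6 months from baseline in both arms and stating the time since the last IMT.

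With the first IMT at baseline, exact 2-week intervals and calendar months, the ambiguity amounts to about 3 against 13 weeks after the last IMT at month 3, and about 16 against 26 weeks at month 6. With 4-week months the month-3 figures are 2 and 12 weeks, and longer intervals shorten the first figure further, possibly to nothing. None of these variations creates a difference between arms.

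The conclusion rests on both arms following the same visit schedule. That is the natural reading of the shared time frame, though the Protocol does not state it outright. Only evidence of separate clocks for the two arms would make this a matter of bias, and the document contains none.
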